1.1 Executive Summary

The potential for nattokinase to “thin” blood and to reduce blood clotting by positive antithrombotic and fibrinolytic effects presents a unique opportunity to safely study such effects on cardiovascular disease (CVD) and cognition. Unfortunately, such studies of antithrombotic and fibrinolytic pathways of prevention have been limited due to lack of safe compounds and the adverse reactions associated with current agents such as Coumadin. Nattokinase, an over-the-counter supplement used for cardiovascular health, is the most active functional constituent of natto, a fermented soy product. Natto has been consumed primarily by the Japanese for over 1000 years, a population with one of the lowest risks for CVD and dementia. CVD and dementia remain the most challenging age-related health risks of the 21st century for Americans necessitating development of further effective preemptive strategies. Whether reducing the propensity for thrombus formation and/or increasing fibrinolytic activity can prevent the progression of atherosclerosis and cognitive decline has not yet been determined.

Using nattokinase under primary prevention conditions, we propose to conduct a randomized, double-blinded, placebo-controlled trial to determine whether decreasing atherothrombotic risk can reduce the progression of atherosclerosis and cognitive decline. We propose to randomize 240 healthy non-demented women and men to nattokinase supplementation or to placebo for three years. The primary trial end points will be measurement of carotid arterial wall thickness and arterial stiffness, early changes of atherosclerosis that can be measured safely by non-invasive imaging techniques. The secondary trial end point will be ascertained through change in cognition measured by a neuropsychological battery. In addition, biochemical blood measurements and in vitro studies will be conducted to compare the effects of nattokinase relative to placebo on blood coagulation and thrombus break-down capabilities, blood flow properties, inflammation and inflammatory activation of endothelial cells that line blood vessels.

At the conclusion of this trial, we expect to have sufficient evidence as to whether reducing propensity for thrombus formation and/or increasing fibrinolytic activity can prevent atherosclerosis progression and cognitive decline. Results will provide novel and important data that will be informative concerning primary prevention through the atherothrombotic pathway. Providing evidence for a reduction in atherosclerosis progression and cognitive decline with nattokinase is likely to shift the current clinical paradigm for the prevention of these chronic age-related processes. Additionally, such evidence will serve to create a new field of discovery and opportunity for prevention of CVD and dementia.

1.2 Objectives and Hypotheses

The goal of the proposed study is to determine under randomized controlled trial conditions whether nattokinase reduces subclinical atherosclerosis and cognitive decline in healthy women and men. Our hypotheses are: 1) Compared to placebo, nattokinase will show less subclinical atherosclerosis progression and cognitive decline in healthy women and men; 2) The reduction in subclinical atherosclerosis progression and cognitive decline with nattokinase will be correlated; and, 3) The reduction in progression of subclinical atherosclerosis and cognitive decline with nattokinase will be mediated through hemostatic, fibrinolytic and hemorheological factors as well as attenuation of inflammation, monocyte activation, vascular endothelium injury and activation of vascular endothelium by circulating monocytes.

1.3 Study Overview

The Nattokinase Atherothrombotic Prevention Study (NAPS) is a randomized, double-blinded, placebo-controlled, non-invasive vascular imaging trial. A total of 240 healthy non-demented women and men without clinical evidence of CVD or diabetes mellitus will be randomized to either placebo or to active oral nattokinase 2,000 fibrinolytic units daily. Recruitment will occur over 2 years and the treatment period will be for 3 years. Candidates will be prescreened, seen for 1 screening visit to determine eligibility and then randomized at a baseline visit. Participants will then return for a follow-up visit 1 week after randomization and then will be followed monthly for the first 6 months and then every 3 months for the remainder of the trial. Rate of change in distal common carotid artery (CCA) far wall intima-media thickness (CIMT) and arterial stiffness in computer image processed B-mode ultrasonograms will be the co-primary trial end points. Cognitive decline determined with a neuropsychological battery designed to evaluate 7 cognitive domains including: attention, concentration, working memory, executive function; visuospatial/visuoconstructive skills; naming/semantic memory; and verbal and nonverbal episodic memory will be the secondary trial endpoint. Other endpoints will include blood pressure, hemostatic, fibrinolytic and hemorheological factors as well as platelet activity and biomarkers for inflammation, monocyte activation, vascular endothelium injury and activation of vascular endothelium by circulating monocytes.

1.4 Inclusion Criteria

[figure not shown]
- (1) Age \geq 55 years
- (2) Male or postmenopausal female (no uterine bleeding for >6 months)

1.5 Exclusion Criteria

- (1) Clinical signs, symptoms, or personal history of CVD
- (2) Diabetes mellitus or fasting serum glucose >140 mg/dL
- (3) Plasma triglyceride levels ≥ 500 mg/dL
- (4) Uncontrolled hypertension (systolic blood pressure >160 mmHg or diastolic blood pressure >110 mmHg)*
- (5) Uncontrolled tachycardia or irregular heart rates (i.e., atrial fibrillation)
- (6) Thyroid disease (untreated)
- (7) Renal insufficiency (defined as serum creatinine >2.0 mg/dL)
- (8) Life threatening illness with prognosis <5 years
- (9) Current use of lipid-lowering medication
- (10) Current use of food supplements containing soy, soy protein, isoflavones or other phytoestrogens
- (11) Known sensitivity or allergy to soy or nuts
- (12) Regular aspirin or other antiplatelet medication use
- (13) Use of anticoagulants
- (14) Bleeding diatheses or tendencies

*Participants who enter screening with a systolic blood pressure >160 mmHg or diastolic blood pressure >110 mmHg will be immediately referred to their physician or to an emergency room. Once the blood pressure is controlled, the participant will become eligible for the trial. Participants who enter screening with mild to moderate hypertension (systolic blood pressure ≤ 160 mmHg or diastolic blood pressure ≤ 110 mmHg) will be notified immediately and a letter issued to the participant and to the participant's physician. Control of hypertension is a requisite to continue into the trial.

1.6

Trial Clinic Flow

- Fasting blood samples drawn for:
 - Chemistry (FSG \leq 140 mg/dL; serum creatinine \leq 2.0 mg/dL)
 - CBC
 - Platelet count
 - Prothrombin time (PT)
 - activated partial thromboplastin time (aPTT)
 - Lipids (triglycerides $<$ 500 mg/dL)
 - C-reactive protein (CRP)
 - Hemoglobin A1c

Draw and store at -80°C (analyze only when eligible):

- Insulin
- Inflammatory markers
 - MCP-1
 - IL-8
 - TNF α
 - IL-1 β
 - IL-10
 - E-Selectin
 - P-Selectin

↓

↓

Schedule randomization visit appointment

8 hour fast

↓

[figure not shown]
↓

Final Eligibility

- Final Eligibility Check List **[Form 17]**
 - ↓
 - ↓

Randomization Visit (v00)

- Nonstudy Medications Record **[Forms 13,14]**
- History of Vitamin and Nutritional Supplement Use Questionnaire **[Form 15]**
- Dietary Food Frequency **[Form 18]**
- Soy Food Questionnaire **[Form 19]**
- 7-Day Physical Activity Questionnaire **[Form 20]**
- Center for Epidemiologic Studies Depression (CES-D) Scale **[Form 21]**
- Cognitive assessment **[Form 22]**
- Vitals signs (systolic blood pressure \leq 160 mmHg and diastolic blood pressure \leq 110 mmHg) **[Form 16]**
- Pulse rate **[Form 16]**
- Weight **[Form 16]**
- Waist:hip measurement **[Form 23]**
- 12-lead ECG **[Form 24]**
- CIMT-2/arterial stiffness
- Fasting blood samples drawn for:
 - Fibrinogen
 - vWF antigen
 - Tissue plasminogen activator (tPA)
 - Plasminogen activator inhibitor-1 (PAI-1)
 - D-dimers
 - Platelet aggregation (ADP, collagen, epinephrine)
 - Ristocetin cofactor
 - Factor VIII

1.7 Schedule of Visits and Laboratory Studies (See Section 7.6 (Table) for specific details)

RESEARCH ACTIVITY	SCREEN	BASELINE	WEEK 1	MONTH												
	01	02	03	04	05	06	09	12	15	18	21	24	27	30	33	36
Chemistry Panel	x			x	x	x	x	x		x	x	x	x	x	x	x
Insulin	x				x			x	x	x	x	x	x	x	x	x
Complete Blood Count	x			x	x	x	x	x	x	x	x	x	x	x	x	x
Platelet Count	x			x	x	x	x	x		x	x	x	x	x	x	x
Prothrombin time (PT)	x			x		x			x	x	x	x	x	x	x	x
Activated Partial Thromboplastin Time (aPTT)	x			x		x			x	x	x	x	x	x	x	x
Fibrinogen		x	x	x				x	x	x	x	x	x	x	x	x
vWF Antigen		x	x	x				x			x			x		
Tissue Plasminogen Activator (tPA)		x	x	x				x			x			x		x
Plasminogen Activator Inhibitor-1 (PAI-1)		x	x	x				x			x			x		x
D-Dimers		x	x	x				x			x			x		x
Platelet Aggregation (ADP, Collagen, Epinephrine)		x		x				x								
Ristocetin Cofactor		x	x	x				x			x			x		x
Factor VIII		x	x	x				x			x			x		x
Nattokinase		x	x	x	x	x	x	x	x	x	x	x	x	x	x	x
Anti-Nattokinase Antibodies		x		x				x			x			x		x
Erythrocyte Sedimentation Rate (ESR)		x	x	x				x			x			x		x
Red Blood Cell Aggregation (Plasma)		x	x	x				x			x			x		x
Red Blood Cell Aggregability (Polymer)		x	x	x				x			x			x		x
Plasma Viscosity		x	x	x				x			x			x		x
Whole Blood Viscosity		x	x	x				x			x			x		x
MCP-1	x				x					x			x			x
IL-8	x				x					x			x			x
TNF α	x				x					x			x			x
IL-1 β	x				x					x			x			x
IL-10	x				x					x			x			x
E-Selectin	x				x					x			x			x
P-Selectin	x				x					x			x			x
Endothelial Injury In-Vitro Assay: VCAM-1, ICAM-1		x			x					x			x			x
Monocyte Activation (FACS): CD11b, CD11c, VLA-4		x			x					x			x			x
Lipids/C-Reactive Protein (CRP)	x								x	x	x	x	x	x	x	x
Hemoglobin A1c	x					x			x	x	x	x	x	x	x	x
Storage		x	x	x	x	x	x	x	x	x	x	x	x	x	x	x
Buffy Coat		x			x				x			x			x	
ApoE Genotype						x										
Urine Dipstick		x		x												

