3.2 Screening

Potential participants will be pre-screened with a Telephone Questionnaire **[FORM 1]** that will cover major inclusion and exclusion criteria. The study will be explained to potential participants at this time.

Individuals fulfilling the Telephone Questionnaire eligibility criteria and interested in the study will be scheduled for the screening visit (SV) and instructed to stop soy, soy protein and isoflavone food supplements one month prior to SV if currently taking any of these products.

Participants will be instructed to fast for 8 hours prior to SV.

Final study eligibility will be determined over SV and the baseline visit (v00).

1 week* 2 weeks
Telephone pre-screening ⇒ SV ⇒ v00 (randomization)

*1 month if potential participant needs to stop soy, soy protein and isoflavone food supplement intake prior to SV.

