3.3 Screening Visit (SV)

A SV appointment is contingent upon fulfilling all pre-screening eligibility criteria **[FORM 1]**. At SV, the following will be performed:

1. Assign study identification (ID) number (see Section 3.4 for procedure)
2. Explanation of study aims, protocol, benefits, risks
3. Participants sign Informed Consent and HIPPA **[FORM 2]**
4. Participants complete forms covering contact and demographic information:
 - Participant Information Form **[FORM 3]**
 - Personal Information Form **[FORM 4]**

5. Pre-screening Telephone Questionnaire **[FORM 1]** eligibility criteria reviewed with participant
6. Ensure that soy, soy protein and isoflavone food supplements have been stopped at least one month prior to SV (see Section 3.2)
7. Administer the Cardiovascular Disease History Questionnaire **[FORM 5]** and confirm that participants have no clinical manifestations of cardiovascular disease.
8. Administer the baseline Bleeding Assessment Questionnaire **[FORM 6a]** and confirm that participants have no bleeding diatheses or bleeding tendencies
9. Participants administered baseline Smoking, Passive Smoking, Alcohol, Other Substance Use Questionnaire **[FORM 7a]**
10. Administer the Reproductive History Questionnaire **[FORM 8]** and confirm that female participants have not menstruated for at least 6 months
11. Participants administered questionnaires covering health information:
 - Medical History Questionnaire **[FORM 9]**
 - Modified Rose Questionnaire **[FORM 10]**
 - Claudication Questionnaire **[FORM 11]**
 - Cardiovascular Disease Risk Factor Assessment Form **[FORM 12]**
12. Administer the Nonstudy Medications Record **[FORMS 13,14]** and confirm that participants are not taking lipid-lowering medication
13. Administer History of Vitamin and Nutritional Supplement Use Questionnaire **[FORM 15]** and confirm that participants are not taking soy, soy protein and isoflavone food supplements
14. Obtain participant's blood pressure and pulse rate **[FORM 16]** and confirm that systolic blood pressure is ≤ 160 mmHg and diastolic blood pressure is ≤ 110 mmHg
15. Obtain and record participant's weight and height **[FORM 16]**
16. Carotid artery ultrasound examination performed (first baseline - see Section 4.2 for randomization procedure)
17. Fasting blood samples drawn and analyzed for:
 - Chemistry
 - CBC
 - Platelet count
 - Prothrombin (PT)/activated partial thromboplastin time (aPTT)
 - Lipids
 - C-reactive protein
 - Hemoglobin A1c

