4.1 Visit 00 (v00)

1. Complete and review Final Eligibility Check List **[FORM 17]** and ensure that all eligibility criteria have been fulfilled before proceeding with randomization
2. Administer the Nonstudy Medications Record **[FORMS 13,14]** and confirm that participants are not taking lipid-lowering medication
3. Administer History of Vitamin and Nutritional Supplement Use Questionnaire **[FORM 15]** and confirm that participants are not taking soy, soy protein and isoflavone food supplements
4. Administer Dietary Food Frequency **[FORM 18]**
5. Administer Soy Food Questionnaire **[FORM 19]**
6. Administer 7-Day Physical Activity Recall Questionnaire **[FORM 20]**
7. Administer Center for Epidemiologic Studies Depression (CES-D) Scale **[FORM 21]**
8. Perform cognitive function assessment **[FORM 22]**
9. Obtain participants' blood pressure and pulse rate **[FORM 16]** and confirm that systolic blood pressure is ≤ 160 mmHg and diastolic blood pressure is ≤ 110 mmHg
10. Obtain and record participant's weight **[FORM 16]**
11. Measure and record waist:hip circumferences **[FORM 23]**
12. Obtain 12-lead ECG **[FORM 24]**
13. Carotid artery ultrasound examination performed (second baseline - see Section 4.2 for randomization procedure)
14. Perform urine dipstick
15. Fasting blood samples drawn and analyzed for:
 - Fibrinogen
 - vWF antigen
 - Tissue plasminogen activator (tPA)
 - Plasminogen activator inhibitor-1 (PAI-1)
 - D-dimers
 - Platelet aggregation (ADP, collagen, epinephrine)
 - Ristocetin cofactor
 - Factor VIII
 - Nattokinase
 - Anti-nattokinase antibodies
 - Erythrocyte sedimentation rate (ESR)
 - Red blood cell aggregation (plasma)
 - Red blood cell aggregability (polymer)
 - Plasma viscosity
 - Whole blood viscosity
 - Endothelial injury in-vitro assay: VCAM-1, ICAM-1
 - Monocyte activation (FACS): CD11b, CD11c, VLA-4
 - Storage
 - Plasma (EDTA) generic storage
 - Plasma (citrate) generic storage
 - Serum generic storage
 - Buffy coat
16. Active nattokinase/placebo nattokinase dispensed **[FORMS 25]**

17. Fill in the **study product ID number item** of the Eligibility Summary section on the Final Eligibility Check List **[FORM 17]** according to the randomization procedures in Section 4.2.

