9.5.2.6 Participant Compliance

For each participant, compliance to the study products will be monitored and summarized in a monthly report. Non-compliance will be reported to the principal investigator. Compliance will be assessed by the following:

- 1) Compliance to active nattokinase and placebo nattokinase will be assessed by capsule count. Compliance will be defined as $\geq 80\%$ of study product consumed. Capsule count will be the primary determinant of compliance.
- 2) Overall study compliance will be determined by number of missed study visits.

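### No eligibility, washout or on-trial text names non-study nattokinase or natto, and no contamination check is planned, so outside use could dilute the contrast without being reported

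*Combined protocol and SAP*

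**What the plan says.** The trial compares two groups "randomized to either placebo or to active oral nattokinase 2,000 fibrinolytic units daily" (section 1.3). Section 1.1 says of the test agent: "Nattokinase, an over-the-counter supplement used for cardiovascular health, is the most active functional constituent of natto, a fermented soy product".

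Exclusion 10 in section 1.5 is "Current use of food supplements containing soy, soy protein, isoflavones or other phytoestrogens". The nearest other exclusions are number 12, "Regular aspirin or other antiplatelet medication use", and number 13, on anticoagulants. Neither names nattokinase.

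The steps that carry out the supplement rule use a shorter list:
- Section 3.2: candidates are "instructed to stop soy, soy protein and isoflavone food supplements one month prior to SV if currently taking any of these products".
- Section 3.3, item 6: "Ensure that soy, soy protein and isoflavone food supplements have been stopped at least one month prior to SV". Item 13 repeats the check using Form 15.
- Section 4.1, item 3: staff use Form 15 to "confirm that participants are not taking soy, soy protein and isoflavone food supplements".

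After randomization, section 1.8 schedules Form 15 (supplements) at the monthly and three-monthly visits and Form 19 (soy foods) periodically. Section 9.2.3.3 schedules plasma nattokinase at v00 and at every later visit. Section 9.2 keeps clinic staff blinded to that result. On compliance, section 9.5.2.6 states: "Capsule count will be the primary determinant of compliance".

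**The concern.** The protocol has a supplement exclusion, a washout and repeated checks, and it applies them to products related to the test agent without naming the agent itself. People who volunteer for a nattokinase heart-health trial are plausible users of the over-the-counter product.

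Two things are at stake. Use shortly before entry would mean that the baseline haemostatic, rheological and stiffness values are not clearly untreated values. Use in the placebo arm during the three years would pull the differences in carotid intima-media thickness (CIMT), stiffness, cognition and the proposed mediators toward zero. The outcome analyses in section 9.6.5 are intent-to-treat whatever the compliance, so any such dilution stays in the primary estimate.

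**Working it through.** **Step 1. Which texts reach non-study nattokinase or natto?**

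- *Exclusion 10:* covers supplements containing soy, soy protein, isoflavones or other phytoestrogens. A nattokinase capsule is caught only if staff judge that it contains soy. Natto eaten as food is not a supplement and is not caught.
- *Section 3.2, SV items 6 and 13, v00 item 3:* cover soy, soy protein and isoflavone supplements. Nattokinase and natto are not named.
- *On-trial text:* no passage tells participants how to treat non-study nattokinase or natto. Forms 15 and 19 record use, with no rule attached.

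**Step 2. Would the planned data reveal outside use, and does the plan use them that way?**

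- *Capsule count:* section 5.2 uses (dispensed − returned) / (capsules per day × days) × 100. Only study capsules enter. A placebo participant who takes every capsule and also buys nattokinase scores as fully compliant, so the analyses in section 9.6.3 restricted to compliance above 80% would keep that person.
- *Plasma nattokinase:* the first sample is drawn at the randomization visit, is not an eligibility criterion, and is hidden from the clinic. It cannot act as an entry screen. Its one named analytic role is as an explanatory variable in the ancillary analyses of section 9.6.7.1.
- *Confounder lists:* section 9.6.3 names dietary genistein, daidzein and glycitein and relevant non-study drugs. Section 9.6.5.1 names dietary nutrients and non-study medications. Neither names non-study nattokinase.

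The data for a contamination check would therefore be collected, but no check is specified.

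**Step 3. How much could it matter?**

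The text reviewed gives 240 participants but no power, effect size, standard deviation or rate of outside use, so there is no planned figure to reproduce. What follows is a sensitivity calculation on assumed inputs: 120 per arm (1:1 allocation assumed), two-sided test, and starting power of 80% or 90%.

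Let c be the share of the placebo arm that receives the full treatment effect for the whole trial, with no extra effect in the active arm. The expected difference is multiplied by (1 − c), so

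power = Φ[(z_α + z_power)(1 − c) − z_α].

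At α = 0.05 and 80%, z_α + z_power = 1.960 + 0.842 = 2.802. For c = 10%: 2.802 × 0.90 − 1.960 = 0.561, and Φ(0.561) = 0.713.

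The total N that restores the starting power is 240/(1 − c)², rounded up per arm. For c = 10%: 120/0.81 = 148.1, so 149 per arm or 298 in total.

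| c | From 80%, α = 0.05 | From 90%, α = 0.05 | From 80%, α = 0.025 | Total N to restore power |
|---|---|---|---|---|
| 2% | 78.4% | 88.8% | 78.2% | 250 |
| 5% | 75.9% | 86.9% | 75.4% | 266 |
| 10% | 71.3% | 83.1% | 70.3% | 298 |
| 20% | 61.1% | 73.7% | 58.9% | 376 |

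The α = 0.025 column shows the case where α is split over two co-primary endpoints. Section 9.6.5 states no α for those tests.

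**The case against.** The best defence has four parts.

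1. *Exclusion 10 may already apply.* Its first term is supplements containing soy, and section 1.1 ties nattokinase to a fermented soy product. Staff could reasonably treat a natto-derived capsule as a soy supplement. Exclusion 13 is not limited to prescription anticoagulants, and section 1.1 presents nattokinase as blood-thinning. This stands in part. A reader might infer that a site would plainly pass a nattokinase user, but the documents show ambiguity, not a clear pass. The ambiguity still matters, because the SV and v00 checks use the narrower list and name no anticoagulant supplement.

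2. *The rule may sit elsewhere.* Forms 1, 15, 17 and 19 and the consent text were not available, and any of them may mention nattokinase. This stands and limits confidence. A form item would still leave the eligibility and on-trial text to be aligned with it.

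3. *Outside use is recorded and measured.* A reader might infer that natto is ignored altogether, or that a null result could never be told apart from a contaminated comparison. Neither is supported. Form 19 records soy foods, section 9.6.3 compares dietary isoflavones between arms, Form 15 records supplements, and plasma levels and periodic anti-nattokinase antibodies are collected. Contamination could be examined afterwards. What is missing is a commitment to do so. The documents also do not say whether the assay detects outside use in samples taken after an 8-hour fast.

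4. *The power losses are hypothetical.* This stands. Intermittent capsules or occasional natto would dilute less than the formula assumes.

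**Conclusion.** The concern holds in a limited form. The plan's wording leaves non-study nattokinase and natto unaddressed at entry, in the washout and during treatment, and it specifies no contamination check from data it will already hold. Outside use in the placebo arm could dilute the between-arm contrasts. That it does so, or by how much, cannot be shown from the documents.

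The power figures rest on an assumed starting power, an assumed c, and full effect throughout. For a given c they are an upper bound on the loss, provided outside use works no better than the study product. They should not be read as the trial's actual power. With use in 5% of the placebo arm the loss from 80% is about 4 points; at 20% it is about 19 points.

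The point deserves a change because it affects who enters and how a null result can be read, and because the change is cheap. Confidence is moderate.

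**What to change.** 1. Reconcile exclusion 10, section 3.2, SV items 6 and 13 and v00 item 3 so that all name non-study nattokinase supplements and natto. Add matching on-trial text on non-study use, with any use recorded on Forms 15 and 19, and check that the forms and consent text agree. The existing one-month soy washout is not evidence for a nattokinase washout; the sponsor should set and justify any length.

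2. Pre-specify in section 9.6 that the DCC, keeping the clinic blinded, tabulates plasma nattokinase at v00 in all participants and at every visit in the placebo arm, together with recorded outside use. Report this with the primary result and state the assay's detection limits in fasting samples.

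Cost: edits to the protocol, forms and analysis plan. A few candidates may be delayed or become ineligible. No new visits or assays are needed.
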